## 20) Analysis populations:

Definition of analysis populations, e.g. intention to treat, per protocol, complete case, safety, and other.

- a. Intent to treat: Those who were randomized to intervention and control groups (regardless of whether or not they received the kit from their "promotor")
- b. Per protocol: Those who were members of a cluster that was randomized to the intervention and meet specific criteria per aim will be part of the per-protocol analysis. For Aim 1, it will be those individuals in the intervention arm who received an HIV self-testing kit. For Aims 2 and 3, it will be those individuals in the intervention arm who received a kit and attended a clinic visit.
- c. Complete case— We will not conduct complete case analyses as we will attempt to use all available data from all participants (see section 29: Missing Data).

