1.3.3 ANALYSIS OF ADDITIONAL ENDPOINT(S)

Primary Outcome: the primary outcome measure will be linkage to care or prevention within 3 months of the Aim 1 intervention start. Linkage will be defined for HIV-positive participants as a documented confirmatory HIV test result, and a documented HIV clinic visit following referral. Linkage will be defined for HIV-negative participants as documented evidence of evaluation for PrEP (following standard of care procedures) extracted from medical records.

Secondary outcome: The secondary outcomes will be confirmatory HIV testing uptake 3 – 6 months after intervention start and the initiation of ART, or PrEP (among those screened as eligible), within 3 months of the confirmatory test or eligibility screening. HIV testing uptake will be measured via documented testing records in clinic records and ART start will be measured via documented prescription for ARV medications, and for PrEP start, via oral PrEP prescription.

Third outcome: The third primary outcome is a composite measure meant to capture "success" in HIV prevention and/or treatment behaviors. The measure will be defined as either adequate levels of tenofovir, indicating PrEP adherence (defined as TFV levels of >= 1500 ng/mL in urine indicating adequate adherence vs. < 1500 ng/ml) among HIV seronegative individuals who screened eligible for PrEP or the proportion of HIV-positive participants with viral suppression (defined as HIV RNA <400 c/mL using the Abbott realTime HIV-1 platform and assay, with a detectable threshold of 40 cells per microliter at 6 months. PrEP adherence will be measured at 6 months after initiation using our novel technology of point-of-care rapid testing to assess TFV adherence in urine (developed by Co-I [name] in collaboration with Alere Rapid Diagnostics[™]). For both components of the measure, we will define missing values as failure (i.e. inadequate adherence or unsuppressed).

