## Section 6: Analysis

# 26) Outcome definitions

- a. Primary Outcomes:
  - i. Proportion of HIV testing: The first primary outcome will be the proportion of study participants who self-report HIV testing in the last three months (at the 3 month follow up visit) compared to those who self-report not using testing during the last three months.
  - ii. Proportion of HIV self-testing: The second outcome will be the proportion of study participants who self-report using the self-testing kit in the last three months (at the 3 month follow up visit) compared to those who self-report not using a self-testing kit during the last three months.
  - iii. Proportion with successful linkage to ART or PrEP within 3 months of intervention start (ie: when promoters receive self-test kits to distribute). The second primary outcome will be defined as the proportion of individuals who link to ART (if confirmatory HIV testing is positive) or PrEP evaluation (if confirmatory HIV testing is negative), meaning they present at a study facility/clinic (depending on results of HIV testing) within three months of the intervention start (defined as from when study promotors receive the kits for distribution).
  - iv. HIV treatment and prevention success: The third primary outcome is a composite measure meant to capture "success" in HIV prevention and/or treatment behaviors (ie: Viral suppression among HIV+ and adequate TFV among those prescribed PrEP). The measure will be defined as either adequate levels of tenofovir, indicating PrEP adherence (defined as TFV levels of <1500 ng/mL in urine indicating inadequate adherence vs. ≥ 1500 ng/ml) among HIV seronegative individuals who screened eligible for PrEP *or* the proportion of HIV-positive participants with viral suppression (defined as HIV RNA <400 c/mL using the Abbott realTime HIV-1 platform and assay, with a detectable threshold of 40 cells per microlitre) at 6 and 12 months. Secondary thresholds of <1000 copies/mL will also be examined. PrEP adherence will be measured at 6 and 12 months after initiation using our novel technology of *point-of-care rapid testing to assess TFV adherence in urine* (developed by Co-I [name] in collaboration with Alere Rapid Diagnostics™). For both components of the measure, we will define missing values as failure (i.e. inadequate adherence or unsuppressed).

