# 28) Missing data:

The study team will employ several strategies to account for and address missing data during the *Owete* trial period. Missing data will be categorized into: 1) missed individual questions, 2) missed visits, and 3) missing clinical data.

- a. Missed individual questions: For instances when participants missed questions as part of a validated scale, we will first assess the amount of missingness by making a variable for the number of questions missed per participant. We will check the assumption of missing at random^11 by tabulating basic socio-demographic characteristics on questions and participants for missing values. For missing questions truly missed at random and comprising less than 20% of the total sub-scale length, however, we will use single imputation. For questions related to alcohol consumption where non-standardized liquid portions and/or alcohol contents were reported, we will use mean imputation to report drinks per day for these participants. In situations where questions that were not part of a sub-set or scale of questions were missing, these variables were left as missing. Information on percent of questions missing and imputed will be reported for each variable as appropriate in study manuscripts.
- Missed visits: When a participant misses a visit this will be noted in the study register. No data will be imputed for this participant for the missed visit.
  Analytic approach: For the primary intent to treat analysis, we will treat missing outcome variables as failure, i.e. utilizing a failure approach for primary outcomes where the values are treated as zero, not missing. For the per-protocol sample, we will either exclude cases with incomplete data or apply multiple imputation techniques.

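### The SAP's Aim 2 per-protocol set admits only intervention men who attended a clinic visit, which is essentially the linkage outcome, so its linkage rate reflects the selection rule and not the intervention

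*SAP*

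**What the plan says.** SAP section 20.b builds the per-protocol population from one arm: "Those who were members of a cluster that was randomized to the intervention and meet specific criteria per aim". The criteria differ by aim. For Aim 1: "For Aim 1, it will be those individuals in the intervention arm who received an HIV self-testing kit". For the later aims: "For Aims 2 and 3, it will be those individuals in the intervention arm who received a kit and attended a clinic visit". The visit has no time window and no required content, and nothing is said about which control men, if any, enter the comparison.

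SAP section 26.a.iii defines the Aim 2 primary outcome as linking to ART or to PrEP evaluation, "meaning they present at a study facility/clinic (depending on results of HIV testing) within three months of the intervention start". The current protocol, section 1.3.3, is narrower. For positives: "Linkage will be defined for HIV-positive participants as a documented confirmatory HIV test result, and a documented HIV clinic visit following referral". For negatives: "Linkage will be defined for HIV-negative participants as documented evidence of evaluation for PrEP", taken from medical records.

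SAP section 28 separates the two populations. "For the primary intent to treat analysis, we will treat missing outcome variables as failure". "For the per-protocol sample, we will either exclude cases with incomplete data or apply multiple imputation techniques". SAP section 27 names no test or comparator for the per-protocol set.

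**The concern.** A per-protocol set should be defined by whether the assigned intervention was delivered or received. Here part of the definition is whether the participant did what the intervention is meant to achieve. A man who took a kit and never went to a clinic is an Aim 2 failure, and the rule removes him. A man who took a kit and linked stays in. The condition is met after randomisation, and it is written for the intervention arm alone.

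The SAP names a per-protocol analysis and gives its sample a missing-data rule, so a result is likely to be produced. If it were reported with the intent-to-treat result, near-total linkage could be taken as support for the intervention when it follows from how the set was chosen.

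**Working it through.** **Inputs.** Control linkage 24%, intervention linkage 39%, ICC 0.15, 40 networks per arm of 8 men (SAP section 11); two-sided 5% test (SAP section 16). The current protocol, section 1.2, has 70 networks per arm of 7. Kit receipt among intervention men is not in the documents; 70% is assumed, with a range of 50% to 100%. The share q of clinic attenders who meet the outcome definition in time is also not given; 1.0, 0.8 and 0.5 are used.

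**The plan's own figure first.** Design effect = 1 + (8 − 1) × 0.15 = 2.05. Effective men per arm = 320 / 2.05 = 156.1. Power for 24% against 39% is 81.7%, in line with the stated 80% or greater. With 70 × 7 the design effect is 1.9, effective men per arm 490 / 1.9 = 257.9, and power 95.8%. The Aim 2 inputs are therefore read correctly.

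**Rate in the per-protocol set.** The quantity is P(linked | intervention, kit, clinic visit) = q.
- Under the SAP definition with the visit inside three months, q = 1 and the rate is 100%. This holds whether true linkage is 24% or 39%. Only the size of the set changes: 320 × 0.70 × 0.24 = 54 men, or 320 × 0.70 × 0.39 = 87 men. At 24% linkage it is 38 to 77 men for kit receipt of 50% to 100%.
- If some visits are late or fail the stricter protocol definition, the rate is q: 80% or 50% in the two examples.

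**Comparator A: all control men.** With no true effect and 24% linkage in both arms, the apparent difference is q − 0.24:

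| q | Per-protocol rate | Apparent difference |
|---|---|---|
| 1.0 | 100% | 76 points |
| 0.8 | 80% | 56 points |
| 0.5 | 50% | 26 points |

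A simulation of 3,000 trials at 40 × 8 used beta-binomial networks with ICC 0.15, 70% kit receipt, no true effect and a cluster-adjusted chi-square. The false rejection rate was 100% at q = 1, 100% at q = 0.8 and 99.5% at q = 0.5. In the q = 1 runs intent-to-treat rejected in 5.8%. Dropping the visit condition and keeping kit receipt gave 5.6%, but only because receipt was simulated as unrelated to linkage.

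**Comparator B: control men who also attended a visit.** If q is the same in both arms, both show the rate q and the difference is zero. A true 24% against 39%, a 15-point effect, would vanish.

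**Aim 1.** With no true effect and 38% testing in both arms (SAP section 11), the per-protocol rate is 0.38 × P(accepts kit | tester) / P(accepts kit). Assume 60% accept a kit:
- every tester accepts: 0.38 / 0.60 = 63%, 25 points above 38%;
- 80% of testers accept: 0.38 × 0.80 / 0.60 = 51%, 13 points above;
- acceptance unrelated to testing: 0.38 × 0.60 / 0.60 = 38%, no bias.

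**The case against.** The strongest reply is that no primary conclusion rests on this set. Protocol section 1.3.2 takes randomised arm, by intent to treat, as the primary predictor, and SAP section 28 calls intent-to-treat primary. SAP section 27 gives the per-protocol set no test, lists no sensitivity analyses, and section 29 requires no additional ones. That stands. A reader might infer that the trial's main Aim 2 result is compromised; the documents do not support that. Nor do they say that the per-protocol result will be printed beside the intent-to-treat result.

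Three further stronger readings also go beyond the text.

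- **That the SAP plans a comparison of 100% with 24%.** It names no comparator. The 76-point figure is one reading, and the documented gap is the missing control rule.
- **That the visit and the outcome are the same event.** The visit has no window or content. A man who came late, or who was not evaluated for PrEP, would enter the set as a failure, so the rate can fall below 100%.
- **That Aim 3 suffers equally.** The visit is not the Aim 3 outcome. Protocol section 8.7 draws specimens from men who linked, and both analysis sections already limit Aim 3 to men on ART or PrEP. Clinic contact is largely built into that denominator, and the documents do not show that the condition removes many further failures.

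On Aim 1, kit receipt is one of the SAP's own exposure measures (section 19.a) and depends partly on promoter delivery, so the bias may be small.

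None of this rescues the Aim 2 rule. With unselected controls the contrast is spurious; with controls selected in the same way it loses the effect.

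**Conclusion.** Wrong as written, for a supportive analysis. The Aim 2 per-protocol rule selects intervention men on what is essentially the linkage outcome and leaves the control arm undefined. The resulting intervention-arm rate is 100% under the SAP definition with an in-window visit, and q otherwise. The spurious difference is up to 76 points if all control men at 24% are the comparator, and 26 points at q = 0.5. These sizes rest on the SAP's 24%, on that choice of comparator, and on assumed values of q. That the rule conditions on the outcome rests on the text alone.

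The Aim 1 rule is also a one-arm post-randomisation selection. Its bias runs from none to 25 points in the illustration, and the upper figure needs both 60% acceptance and every tester accepting.

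**What to change.** In SAP section 20.b, delete the clinic-visit condition. Define the per-protocol set by delivery or exposure, with a matching rule in both arms, and name the comparator. One option is to keep networks whose promoter completed the arm's training and was given the arm's materials (kits and transport vouchers, or facility vouchers), with all randomised members counted. Individual exposure with a matching control rule, or a complier-type estimate that keeps all randomised men, are alternatives; simple kit or voucher receipt is unbiased only if receipt is unrelated to the outcome. Label the analysis supportive. Report kit receipt and clinic attendance as fidelity measures, where the table in SAP section 19 already places them.

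The cost is mostly SAP wording. There are two downsides. The network-level set may be close to the intent-to-treat set if delivery is good. The fidelity table has training sign-in sheets and kit distribution records but no record of control vouchers handed to promoters, so that handout must be logged or training attendance used instead.

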## Section 5: Trial Population

**21)** Screening Data: We will report the screening data to describe representativeness of trial sample by age, cluster size, education, and other demographic characteristics by trial arm and beach community.

**22)** Eligibility: Eligibility criteria is outlined below.

In order to participate in the study individuals must meet all of the following criteria:

- 1. Adult (18 years or older)
- 2. Male
- 3. Working as a fisherman or fishing support occupation (e.g. net repairers, boat builders etc.)
- 4. Willing and able to provide informed consent for participation
- 5. Not participating in another research study related to HIV testing, treatment and/or prevention

Criteria for exclusion of subjects:

- 1. Younger than 18 years of age
- 2. Female
- 3. Included in another study on HIV/AIDS
- 4. Inadequate cognitive and/or hearing capacity to complete planned study procedures, at the discretion of the study team
- **23)** Recruitment information to be included in the CONSORT flow diagram.

### 24) Withdrawal/follow-up

- d. Level of withdrawal, e.g. from intervention and/or from follow-up
  - i. Reasons for withdrawal might be that an individual moves out of the area, begins work at a different beach or in a different industry, decides they no longer wish to participate, or are simply lost to follow up. We will attempt to document all reasons for withdrawal.
- e. Timing of withdrawal/LTFU data
  - i. Withdrawal can happen at any time however will be documented best at each study assessment/visit.
- f. Reasons and details of how withdrawal/LTFU data will be presented

i. These will be noted in the CONSORT diagram and tables by study arm and beach community.

## **25)** Baseline patient characteristics

We will evaluate several socio-demographic and clinical characteristics at baseline by which we will describe our study sample. These are outlined in Table 1 below. We will stratify these characteristics by intervention and control arms and report median and the inter-quartile range for continuous variables and the N and percent for categorical and dichotomous variables. No significance testing or p-values will be conducted or reported per CONSORT guidelines.

Table 1: Baseline characteristics of Owete participants, by study arm					
Socio-demographic	Age, sex, household size, marital status, polygamous marriage or not, educational attainment, livelihood strategies/ main income sources, household assets, health behaviors and characteristics (general health status, alcohol use, sexual behavior, mental health status).				
Clinical outcomes	HIV status, ART Status, PrEP Status.				
Network structure	(Add in section for characterization of network structures and membership – details to be obtained from [name]).				

## Section 6: Analysis

# 26) Outcome definitions

- a. Primary Outcomes:
  - i. Proportion of HIV testing: The first primary outcome will be the proportion of study participants who self-report HIV testing in the last three months (at the 3 month follow up visit) compared to those who self-report not using testing during the last three months.
  - ii. Proportion of HIV self-testing: The second outcome will be the proportion of study participants who self-report using the self-testing kit in the last three months (at the 3 month follow up visit) compared to those who self-report not using a self-testing kit during the last three months.
  - iii. Proportion with successful linkage to ART or PrEP within 3 months of intervention start (ie: when promoters receive self-test kits to distribute). The second primary outcome will be defined as the proportion of individuals who link to ART (if confirmatory HIV testing is positive) or PrEP evaluation (if confirmatory HIV testing is negative), meaning they present at a study facility/clinic (depending on results of HIV testing) within three months of the intervention start (defined as from when study promotors receive the kits for distribution).
  - iv. HIV treatment and prevention success: The third primary outcome is a composite measure meant to capture "success" in HIV prevention and/or treatment behaviors (ie: Viral suppression among HIV+ and adequate TFV among those prescribed PrEP). The measure will be defined as either adequate levels of tenofovir, indicating PrEP adherence (defined as TFV levels of <1500 ng/mL in urine indicating inadequate adherence vs. ≥ 1500 ng/ml) among HIV seronegative individuals who screened eligible for PrEP *or* the proportion of HIV-positive participants with viral suppression (defined as HIV RNA <400 c/mL using the Abbott realTime HIV-1 platform and assay, with a detectable threshold of 40 cells per microlitre) at 6 and 12 months. Secondary thresholds of <1000 copies/mL will also be examined. PrEP adherence will be measured at 6 and 12 months after initiation using our novel technology of *point-of-care rapid testing to assess TFV adherence in urine* (developed by Co-I [name] in collaboration with Alere Rapid Diagnostics™). For both components of the measure, we will define missing values as failure (i.e. inadequate adherence or unsuppressed).

## b. Secondary Outcomes:

- v. Retention on ART or PrEP at 6 and 12 months: Using clinic records, we will assess whether men who initiated PrEP and ART attended scheduled appointments, and will compare them to those who were either prescribed PrEP or tested positive for HIV.
- **27)** Analysis methods: Analysis methods to be used and how the treatment effects will be presented:
  - Aim 1: For the test of the intervention effect on the primary outcome of self-reported HIV testing in past 3 months, we will utilize a cluster adjusted Pearson's Chi-square test comparing the proportion of subjects self-testing in the intervention versus the control arm. In secondary analysis we will utilize multilevel mixed-effects logistic regression with cluster adjusted standard errors and a binary outcome of reported HIV self-testing or not (including cluster as one of the levels with random effects allowed). We will investigate factors that influence the probability of success of HIV self-testing, including characteristics of clusters (the close social networks' size and composition, metrics of connectedness, mean cluster self-testing rate), characteristics of the cluster's promoter (age, marital status, HIV status, ART/ PrEP status, measures of the promoter's ties to close-social-network cluster members), and individual level characteristics (demographics, SES, prior HIV testing, self-reported HIV risk, and other health behaviors and characteristics).
  - b. Aim 2: For the test of the social network-central promoters and small incentive intervention effect on the primary outcome of linkage to care or prevention within 3 months of intervention start we will utilize a cluster adjusted Pearson's Chi-square test comparing the proportion of subjects with documented linkage to care or prevention in the intervention versus the control arm. In secondary analysis we will utilize multilevel mixed-effects logistic regression as described in Aim 1 to investigate factors that influence the probability of success of linkage to care and prevention. We will also evaluate the secondary outcomes of ART initiation among HIV-positive persons not currently on treatment, and initiation of PrEP among HIV-negative persons who screen as eligible. We will compare the initiation proportions between study arms using cluster adjusted Chi-square tests and additional multilevel mixedeffects logistic regression to identify influencing factors.
  - c. Aim 3: We will utilize a cluster adjusted Pearson's Chi-square test comparing the proportion of successes (HIV viral suppression and adequate TFV levels) among men (on ART and PrEP, respectively) in the intervention and control networks. For the outcome of retention on ART or PrEP at 12 months, we will utilize a cluster adjusted Pearson's Chi-square test comparing the proportion of subjects on ART or PrEP at 3 months post-trial start who are retained in care at 12 months in intervention versus control group. In secondary analysis we will utilize Cox proportional hazards regression to investigate factors that influence time to discontinuation of ART or PrEP based on clinic visits and chart abstraction. We will also use multilevel mixed-effects logistic regression to investigate factors that influence the probability of viral suppression and TFV detection in urine.
  - d. Any adjustment for covariates: Randomization should yield equivalence between arms on covariates, but if non-equivalence is found on baseline measures or from differential attrition, we will control for it by including the covariate in the model.
  - e. Methods used for assumptions to be checked for statistical methods: Distributional assumptions for outcome variables will be checked using descriptive statistics. For mediation models, the assumption of no interaction between exposure (i.e., intervention vs. control) and mediators will be checked using product terms. Transformations will be used for continuous outcome variables that are skew to obtain more symmetric distributions.
  - f. Any planned sensitivity analyses for each outcome, where applicable:

Not applicable.

g. Any planned subgroup analyses for each outcome including how subgroups are defined: NA

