1.3.2 ANALYSIS OF THE PRIMARY ENDPOINT(S)

Primary Outcome: The primary outcome will be self-reported HIV testing in the past 3 months by participants, as measured in the 3-month follow-up surveys.

Primary Predictor: Cluster (social network) Randomized Arm (intent-to-treat), Intervention or Control.

Analytic Plan: For the test of the intervention effect on the primary outcome of self-reported HIV testing in past 3 months, we will utilize a cluster adjusted Pearson's Chi-square test comparing the proportion of subjects' HIV testing in the intervention versus the control arm. In secondary analysis, we will utilize multilevel mixed-effects logistic regression with cluster-adjusted standard errors and a binary outcome of reported HIV testing or not (including cluster as one of the levels with random effects allowed). We will

investigate factors that influence the probability of success of HIV testing, including characteristics of clusters (the close social networks' size and composition, metrics of connectedness, mean cluster self-testing rate), characteristics of the cluster's promoter (age, marital, HIV, ART, PrEP status, measures of the promoter's ties to close-social-network cluster members), and individual level characteristics (demographics, SES, prior HIV testing, duration in boat crew, self-reported HIV risk).

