## Section 3: Study Methods

## 9) Trial design:

In Aim 1, following the study pilot, community selection, and preparation (see 'recruitment and retention plan') the study team will conduct a census/BMU registry verification in study communities to identify the population of men eligible for the study. We will screen, recruit and enroll eligible men who give their informed consent to participate, then measure their close social networks and baseline characteristics. We will identify network-central, highly-connected men ("promoters") and randomize their close social networks 1:1 to intervention and control groups. Promoters in the intervention group will receive HIVST training, multiple HIVST for distribution to other men, and a small amount of remuneration. Promoters in the control group will receive basic HIV education and training about the study, and will be given vouchers that can be exchanged for HIV tests (standard or free HIVST kits) at nearby health facilities. Using follow-up survey data, we will test the hypothesis that a higher rate of HIV testing will be observed after 3 months among men in networks that receive the intervention compared to control.

In Aim 2, we will test whether network-central promoters can enhance linkage to ART and PrEP (including screening and uptake) after HIV testing among men in their close social networks. Promoters in the Aim 1 intervention group will be asked to distribute information and transport vouchers for ART or PrEP when distributing HIV self-tests to men in their close social networks. We will use clinic data (abstracted from MOH records by the study staff) to test the primary hypothesis that the intervention will result in higher rates of linkage to ART or PrEP (confirmatory testing and ART referral for positives, and PrEP screening for negatives). We also will test the hypothesis that higher ART and PrEP uptake will be observed within 3 months (+ or – about one month) in the intervention group.

In Aim 3, we will measure 6- (+/– about 1 month) and 12-month (+/– about 1 month) VL tenofovir levels using routine viral load testing and a novel point of care PrEP adherence assay (an antibody-based assay permitting measurement of tenofovir levels in urine) among men living with HIV and initiating ART and those HIV-seronegative men initiating PrEP in study sites, respectively, and test the hypothesis that higher rates of virologic

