#### 11) Statistical Power:

**Aim 1:** We calculate that the study will have an 80% or greater power to detect a significant difference in the proportion of HIV self-testing associated with the intervention arm, assuming a proportion self-testing in the control arm of 38% (*observed data from SEARCH study in fishermen*) if the proportion testing in the intervention arm is 52% or greater (odds ratio of 1.8), calculated using an Intraclass Correlation Coefficient (ICC) of 0.15 (*conservative based on SEARCH data*), 40 clusters each in the intervention and control arms, average cluster size of 8 in both arms, and a type-1 error rate of 5%. Figure 2 shows statistical power and the range of detectable odds ratios over extremes of clustering effects.

**Aim 2:** For the Aim 2 combined primary outcome of successful linkage to ART or PrEP within 3 months of intervention start, defined as when the promotor receives the kits at the end of the promotor training which will be upon completion of the baseline survey for that beach. This study will have a 80% or greater power to detect a significant increase in successful linkage, assuming a proportion successfully linked at 3 months in the control arm of 24% (*based on observed SEARCH trial linkage rates weighted for the number of eligible PrEP HIV-negative men and HIV positive men not currently in HIV care*) if the observed proportion in the intervention arm is 39% or greater (odds ratio of 2.0), using an ICC of 0.15, 40 clusters each in intervention and control arms, a cluster size of 8 in both arms, and a type-1 error rate of 5%. Statistical power for combined ART or PrEP start is similar, with a reduction in anticipated eligible numbers per cluster reduced to 6 resulting in a small increase in the detectable odds ratio to 2.2 or greater. Power for a separate analysis of ART initiation alone is likely to be low given the small numbers of new HIV infections in the study sample with odds ratios in excess of 3 or 4 required.

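### SAP section 27 names any HIV testing as the Aim 1 primary outcome but specifies the test on self-testing, so a change of test type with no rise in testing could be declared a success.

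*SAP*

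**What the plan says.** SAP section 26 lists two testing outcomes under its primary heading. Item a.i reads: "The first primary outcome will be the proportion of study participants who self-report HIV testing in the last three months". Item a.ii reads: "The second outcome will be the proportion of study participants who self-report using the self-testing kit in the last three months". Linkage (a.iii) is then called the second primary outcome and the composite (a.iv) the third, so the numbered primaries are a.i, a.iii and a.iv, and the rank of a.ii is unclear.

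SAP section 27, Aim 1, introduces its test as the one for the primary outcome of self-reported HIV testing in the past three months. It then defines the chi-square comparison as "comparing the proportion of subjects self-testing in the intervention versus the control arm". The secondary mixed model takes "a binary outcome of reported HIV self-testing or not" as its outcome. The Aim 1 power statement in SAP section 11 is framed as power to "detect a significant difference in the proportion of HIV self-testing associated with the intervention arm".

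Other places point to testing by any method. SAP section 9 says "we will test the hypothesis that a higher rate of HIV testing will be observed after 3 months among men in networks" receiving the intervention. Protocol section 1.3.2 says "The primary outcome will be self-reported HIV testing in the past 3 months by participants", and its matching test sentence compares "HIV testing in the intervention versus the control arm".

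**The concern.** The two variables are not interchangeable: SAP section 26 defines them separately. The arms also differ by design in access to kits. Under Protocol section 8.5, intervention promoters receive kits to hand to men in their network, whereas control promoters distribute a voucher of no monetary value pointing to facilities that offer a self-test or a standard test. A control man who takes a standard test meets a.i but is a non-tester under the comparison in SAP section 27.

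The intervention can therefore raise self-testing by moving men from one kind of test to another, with no more men tested. An analyst who codes the comparison as written could report success on Aim 1 when its question, whether testing uptake increases, has the answer no. No other planned analysis would expose this: SAP section 27.f lists no sensitivity analyses and section 29 requires no additional ones.

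**Working it through.** **Step 1. The texts side by side.**

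| Place | Variable |
|---|---|
| SAP 8, Aim 1 objective | HIV testing uptake |
| SAP 9, Aim 1 hypothesis | HIV testing |
| SAP 26.a.i | HIV testing |
| SAP 26.a.ii | Use of the self-testing kit |
| SAP 27 Aim 1, outcome named | HIV testing |
| SAP 27 Aim 1, chi-square comparison | Self-testing |
| SAP 27 Aim 1, mixed model | Self-testing |
| SAP 11 Aim 1, difference powered | Self-testing |
| Protocol 1.2 Aim 1, difference powered | HIV testing |
| Protocol 1.3.2, chi-square and mixed model | HIV testing |

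The 38% control rate is labelled self-testing in both SAP section 11 and Protocol section 1.2, although Protocol 1.2 uses it to power HIV testing.

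**Step 2. Inputs and the plan's own power figure.** From the documents: ICC 0.15; two-sided 5% level (SAP 16); 40 clusters of 8 per arm (SAP 11) or 70 clusters of 7 (Protocol 1.2).

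- Design effect = 1 + (m − 1) × ICC. For 40×8: 1 + 7 × 0.15 = 2.05. For 70×7: 1 + 6 × 0.15 = 1.90.
- Effective n per arm = clusters × m / design effect. For 40×8: 320 / 2.05 = 156.1. For 70×7: 490 / 1.90 = 257.9.
- Power for 38% against 52% (pooled two-proportion z-test): 70% at 40×8 and 89% at 70×7. The stated 80% or greater is met by the protocol's numbers but not by the SAP's. The SAP shortfall is a separate matter and does not affect this point.

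**Step 3. Chance of a favourable result when testing does not change.** Assume 38% of men test by some method in both arms. The self-testing proportion is then 0.38 × the share of tests that are self-tests. The probability that the test favours the intervention is Φ[(p₂ − p₁ − 1.96 × SE₀) / SE₁], where p₁ is control, p₂ is intervention, p̄ is their mean, SE₀ = √(2p̄(1 − p̄)/n) and SE₁ = √((p₁(1 − p₁) + p₂(1 − p₂))/n).

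Worked example, shares 50% and 75%, 40×8: p₁ = 0.19, p₂ = 0.285, SE₀ = 0.0482, SE₁ = 0.0479. The argument is (0.095 − 1.96 × 0.0482)/0.0479 ≈ 0.01, giving 50%.

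| Share of tests that are self-tests, control → intervention | p₁, p₂ | 40×8 | 70×7 |
|---|---|---|---|
| 75% → 90% | 0.285, 0.342 | 19% | 29% |
| 50% → 75% | 0.190, 0.285 | 50% | 72% |
| 25% → 50% | 0.095, 0.190 | 67% | 87% |
| 25% → 75% | 0.095, 0.285 | 99% | over 99% |
| Any HIV testing tested instead | 0.38, 0.38 | 2.5% | 2.5% |

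**Step 4. Checks.** A beta-binomial simulation (20,000 trials, cluster-adjusted chi-square with estimated ICC) gives, in the same order, 20% / 29%, 50% / 72%, 68% / 88%, 99% / over 99% and 2.6% / 2.6%. If any testing is 60% in both arms, the 75% → 90% case gives 36% / 53% and the 25% → 75% case gives over 99% at both designs.

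**The case against.** The best defence is that the intended outcome is already clear. SAP 26.a.i labels any testing the first primary outcome, the disputed sentence opens by naming it, and SAP section 17 says the primaries were established in the protocol. The protocol supplied (version 11.0, November 2022) is later than SAP V1 (September 2021), which cites protocol version 4.0, and it uses HIV testing throughout its endpoint and test. On this view the SAP wording is merely out of date. That explains how the conflict may have arisen but does not resolve it: the SAP states no rule that the protocol prevails, and self-testing appears in its chi-square test, its mixed model and its power statement, so it is more than one stray word.

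Second, the illustration is hypothetical. The shares are invented, the 38% is labelled self-testing in both documents, net testing is assumed unchanged, and an ICC of 0.15 is applied to self-testing. Kits reach intervention men through one promoter per network, so self-testing could cluster more strongly, which would lower the figures when a difference is present. All of this stands as a limit on the numbers. It does not touch the contradiction.

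Third, self-testing may be a genuine target: the protocol abstract speaks of increasing self-testing, Protocol section 6.1 of increasing testing with self-tests, and SAP 26 places a.ii under its primary heading. That supports giving it an analysis. It does not make it the test of a.i, and neither the protocol's outcome list nor its analysis sections give a self-testing primary outcome.

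**Conclusion.** The concern holds. The specified comparison for the first primary outcome uses a different variable from the one that defines it, and no comparison in SAP section 27 is specified on any HIV testing. This rests on the text alone.

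The size depends on assumptions. With no effect on testing, and across the self-test shares tried, the chance of a favourable finding runs from 19% to 99% at the SAP's design and from 29% to over 99% at the protocol's, against 2.5% for the correct variable. These figures take 38% as the any-testing rate in both arms. The documents give no split of tests by type, so the range shows what could happen and is not a forecast. It must be fixed before analysis because it decides which variable the primary test uses.

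**What to change.** - In SAP section 27, Aim 1, replace self-testing with HIV testing by any modality in both the chi-square test and the mixed model, matching SAP 26.a.i and Protocol 1.3.2.
- Make the same change in the Aim 1 power statement in SAP section 11.
- Label the self-testing comparison (26.a.ii) as a secondary or process outcome with its own analysis line. This fits the protocol, which lists no self-testing primary outcome.
- State in SAP section 11 and Protocol section 1.2 whether the 38% control rate is any testing or self-testing.

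The cost is wording only. Both items are already defined at the 3-month visit, so no new data are needed.
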